9.3. Exploratory endpoints

1. Exploratory biomarkers (measured every 3 months)

- Markers of endothelial function (Endothelin, VCAM) and
- Antioxidant stress biomarkers (cortisol, malondialdehyde, nitric oxide and glutathione).
- Inflammatory markers: Complete blood count with ESR, hsCRP, uric acid, IL-6, AGE (advanced glycation end products)
- Other Blood parameters: ferritin, vitamin B12, folic acid, other vitamins and minerals, electrolytes, testosterone and estradiol.

2. Hypertension mediated organ damage (Brain, cardiac, kidney and eye)

New onset end organ damage will be assessed as follows:

- Major adverse Cardiac outcomes such as occurrence of MI, TIA, stroke if any throughout the study period
- Hypertensive retinopathy assessed by fundus examination at baseline, 1 year and end of 2 years
- Cognitive assessment will be performed using Montreal Cognitive assessment (in patients 60 and above)

The Montreal Cognitive Assessment (MoCA) is a rapid screening instrument for mild cognitive dysfunction. It assesses different cognitive domains: attention and concentration, executive functions, memory, language, visuo-constructional skills, conceptual thinking, calculations, and orientation. Time to administer the MoCA is approximately 10 minutes. The total possible score is 30 points; a score of 26 or above is considered normal.

- Renal assessment by decline in eGFR

10. Criteria for withdrawal from study

Patients will be withdrawn from the study if they meet any of the following criteria:

- In case of hypertensive emergency or uncontrolled blood pressure
- Patient not willing to continue in the trial
- Patient not compliant with dietary instructions.
- Impaired hepatic function: AST/ALT $\geq 3.0 \times$ ULN
- Impaired renal function: eGFR ≤ 40 mL/min/1.73 m²
- Development of any major adverse cardiac events (angina, MI, stroke etc)

11. Safety assessment

All patients will be continuously monitored for safety from the time of enrollment till the end of study. Safety will be assessed by looking for symptoms of raised blood pressure, periodic blood pressure monitoring and blood tests (liver and renal function test).

Patients will be educated to be aware of warning symptoms such as headache, palpitations, chest pain etc and immediately report to the health coach or treating physician. Patients will also be trained for home based blood pressure monitoring and contact the treating physician if the blood pressure is over 160/100 mm Hg. Blood tests for safety assessment such as liver and renal function tests will be done every 3 months.

12. Statistical considerations

12.1. Sample size calculation

Sample size is calculated based on the expected difference in mean reduction in systolic blood pressure at the end of 1 year between the 2 groups.

Based on an expected difference in mean reduction SBP from baseline to 1 year between the 2 groups as 5 mm Hg and standard deviation of 13 mm Hg, with power 80% and 5% alpha error, having 1:2 allocation ratio the estimated sample size is **83 in standard care arm and 166 in the intervention arm**. Accounting for an additional 20% drop out the final numbers are **104 in standard care and 208 in the intervention arm**.

12.2 Statistical analysis plan

All quantitative variables will be assessed for the normality by Shapiro-Wilk's test. If they follow Gaussian distribution, then they will be expressed as mean + SD. Continuous or quantitative variables which wouldn't follow normal distribution, will be transformed into logarithms or square root. Again, normality will be assessed by Shapiro-Wilk's test. Those variables which will not be following normal distribution after transformation will be represented by median (Interquartile range). Qualitative variables will be expressed as counts and percentages. Analysis will be carried out for the Intention to treat population as well per protocol population. Missing observations will be handled with imputation techniques. Comparison of quantitative data between the intervention group and control group will be done by independent sample 't' test, if they follow normal distribution. Non-normally distributed quantitative variables will be compared by Mann-Whitney U test. Comparison of categorical variables between groups was done by either Chi-square test or Fisher's Exact test based on the number of observations available. ANOVA will be used to compare the mean of normally distributed continuous variables across more than two categories. Equivalent non-parametric test viz, Kruskal Wallis H test will be used to compare non normally distributed continuous variables. Paired 't' test or Wilcoxon Signed Rank test will be used to compare pre and post continuous variables within the groups based on their normality. Exploring the possibilities of doing regression models with covariates. Data capturing and automation will be taken care of by Tableau Software. Microsoft Excel will be used to cross validate the data collected. Data validation and analysis will be carried out by IBM SPSS Statistics for Windows Ver 28.0; Armonk; NY; IBM Corporation. For statistical significance, two tailed p values <0.05 will be considered.

13. Ethical considerations

Study will be initiated after ethics committee approval and after obtaining written informed consent.

Possible benefits

The study may directly benefit the patient as well as the society. The anticipated benefits are improvement in blood pressure control, decrease in the number of antihypertensive

medications, body weight and complication rates of hypertension along with an overall improvement in the quality of life.

Risks involved

The study can have minimal risks due to tapering of antihypertensive medications. It may lead to rise in blood pressure and development of symptoms such as headache, chest pain, etc. However, since dose reduction will be done gradually and blood pressure will be closely monitored we do not anticipate any safety concerns.

14. Reporting of adverse events

Events that are both serious and unexpected for the patient population under study and that occur in participants treated with study medication will be reported to the sponsor/ Institute ethics committee. Adverse events that are not serious, but which lead to permanent discontinuation of study medication will be recorded and included in the final study report. All serious adverse events will be notified to the ethics committee and sponsor as per the timelines of the local IRB/ regulations.

An Adverse Event is any untoward medical occurrence in a patient that may or may not have a causal relationship to the study medication. It may be an unfavorable and unintended sign; symptom or medical condition occurring after the informed consent form is signed. Medical conditions/diseases present before consent is signed are considered AEs if they worsen after consent is signed. Information about every AE will be collected and recorded on the CRF. Adverse events, whether reported by the subject, information received during general discussion by the Principal Investigator, or detected through physical examination, laboratory test or other means will be recorded on the CRF and followed carefully until they resolve.

Abnormal laboratory values or test results should not generally be considered AEs, unless they induce clinical signs or symptoms or require therapeutic intervention; then, they should be recorded on the CRF with an appropriate justification.

Each AE will also be described by:

1. its duration (start and end time and date)
2. the severity grade (mild, moderate, severe)
3. its relationship to the study intervention (none, possible, probable, definite)
4. The action(s) taken by the Principal Investigator.

The severity grade of an AE provides a qualitative assessment of the extent or intensity of an AE, as determined by the investigator or as reported by the subject. The severity grade does not reflect the clinical seriousness of the event, only the degree or extent of the affliction or occurrence (e.g. severe nausea, mild seizure), and does not reflect the relationship to study supplement.

15. Regulatory considerations

The study does not involve use of any investigational drug product and is considered as a non regulatory trial.

The study will be conducted in accordance with the protocol and with the following:

- Applicable ICH GCP guidelines
- Applicable laws and regulations (National ethical guidelines for biomedical and health research involving human participant)

The protocol, amendments, informed consent forms and other relevant documents must be reviewed and approved by the sponsor, submitted to an IRB/IEC by the investigator, and reviewed and approved by the IRB/IEC before the study is initiated.

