4.1. Primary Objective

1. To compare the mean change in systolic and diastolic 24 hr blood pressure ambulatory from baseline to 1 year between the 2 groups
2. To compare the mean change in systolic and diastolic blood pressure clinic based from baseline to 1 year between the 2 groups

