7.5.1 Ambulatory blood pressure monitoring

For all patients ambulatory blood pressure monitoring will be done at monthly intervals for the first 3 months followed by every 3 months till the end of study and also as required by the primary treating physician.

Each measurement will be done for 24 hours. The following criteria will be used for adequacy of measurement (O'brien et al)

- 24 hr reading with > 70% of expected measurements
- 20 valid awake readings
- 7 valid readings at sleep

The frequency of measurement will be half hourly in day time and hourly at night time. Day time and sleep time will be defined based on the sleep time reported by the patient. Activity of the patient along with the time of food intake and medications will be captured during the ambulatory blood pressure monitoring.

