9.1 Primary endpoint

1. Primary outcome will be change in blood pressure as measured by ambulatory blood pressure monitoring at the end of 1 year
2. Primary outcome will be a change in blood pressure as measured in the clinic at the end of 1 year

Ambulatory blood pressure monitoring

Measurements will include mean 24h systolic and diastolic pressures, and daytime values (measured every 30 min from 07:00 am to 10:00 pm) and night-time values (measured every 60 min from 10:00 pm to 07:00 am). Only ambulatory BP recordings with a minimum of 70% measurements will be considered as successful.

In Clinic or office blood pressure: Average of 3 readings measured in the morning with 1 min gap at baseline and end of the study will be considered. Procedure for measurement of blood pressure is detailed under section 6.5 Blood pressure monitoring

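### Section 12.2 lets a normality pre-test on the outcome data choose the scale and test for the primary blood pressure changes, with a fallback that does not estimate the stated mean difference and no committed baseline adjustment

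*Protocol*

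**What the plan says.** The first primary objective (Protocol 4.1) is "To compare the mean change in systolic and diastolic 24 hr blood pressure ambulatory from baseline to 1 year between the 2 groups", and the second asks the same of clinic pressure. Section 9.1 makes both endpoints changes: "Primary outcome will be change in blood pressure as measured by ambulatory blood pressure monitoring at the end of 1 year" and "Primary outcome will be a change in blood pressure as measured in the clinic at the end of 1 year". With systolic and diastolic pressure each, that is four primary comparisons. Section 12.1 sizes the trial on a difference in mean systolic reduction.

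Section 12.2 names no separate primary analysis. It applies Shapiro-Wilk to every quantitative variable. Those that fail "will be transformed into logarithms or square root" and are tested again. For the between-group test, "Comparison of quantitative data between the intervention group and control group will be done by independent sample" t-test where the data are normal. Otherwise, "Non-normally distributed quantitative variables will be compared by Mann-Whitney U test". Covariates appear once: "Exploring the possibilities of doing regression models with covariates".

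Section 7.1 has clinic and ambulatory pressure measured at baseline, before randomisation. Section 7.5.1 adds interim ambulatory recordings: "For all patients ambulatory blood pressure monitoring will be done at monthly intervals for the first 3 months followed by every 3 months".

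**The concern.** Objective, sample size and analysis should refer to the same quantity. Here 4.1 and 12.1 fix a difference in mean change in mm Hg, while 12.2 makes the scale and the test depend on a significance test of the outcome's shape. Three consequences follow.

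- The transformation does not suit the variable. A change is signed, and neither log nor square root is defined for a negative one (nor log for zero).
- The fallback answers another question. Mann-Whitney compares the ordering of patients between arms. It gives no difference in means unless further assumptions are made.
- The rule runs variable by variable, so 24-hour systolic, 24-hour diastolic, clinic systolic and clinic diastolic could be reported with different tests and on different scales.

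Separately, the baseline value is available for everyone but is not committed to the model. That gives up precision and leaves the comparison open to chance baseline imbalance in an open-label trial, where choosing an adjusted or unadjusted analysis afterwards is hard to defend.

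**Working it through.** **Inputs.** From 12.1: difference 5 mm Hg, SD 13 mm Hg, power 80%, alpha 5%, allocation 1:2, 83 and 166 evaluable patients, 20% dropout. From 12.2: two-sided testing. Not in the protocol, so assumed: the mean reduction in each arm, the correlation rho between baseline and 1-year pressure, equal variances at the two times, and the distribution shapes in step 3. SD 13 is read as the SD of the change because 12.1 attaches it to the mean reduction; the text does not say so outright.

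**1. The plan's own figure.** For a two-sample t-test, the noncentrality is 5 / (13 × sqrt(1/n1 + 1/n2)).
- Exact noncentral-t calculation: 80% power needs 81/162. The stated 83/166 is within a few patients of this.
- At 83/166 the noncentrality is 2.86 and power is 81.3%.
- Dropout: 83/0.8 = 103.75, giving 104; 166/0.8 = 207.5, giving 208. Both match.

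The sample size is therefore consistent with an unadjusted t-test on change.

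**2. How many changes cannot be logged or rooted.** Take reductions as normal with SD 13. The share at or below zero is Phi(−mean/13).
- Mean reduction 5: Phi(−5/13) = 0.35.
- Mean reduction 10: Phi(−10/13) = 0.22.
- Standard care at 5 and intervention at 10: 83 × 0.350 + 166 × 0.221 = about 66 of 249 patients.
- Standard care at 0, 10 or 15, with intervention 5 higher each time: about 100, 39 and 21 patients.

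Some patients would be affected under each of these assumptions.

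**3. How easily the transformation step is triggered.** Simulated Shapiro-Wilk rejection at n = 249:

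| Assumed shape of the change | Rejection |
|---|---|
| Exactly normal | about 5% |
| t, 10 df | about 41% to 43% |
| t, 8 df | about 56% |
| t, 5 df | about 88% to 89% |
| Skewness 0.5 (gamma) | about 81% |

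Even with four exactly normal variables, the chance that at least one is rejected would be 1 − 0.95^4 = 18.5% if they were independent. They are correlated, so this is only a guide.

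**4. What baseline adjustment is worth.** With equal variances, ANCOVA variance / change-score variance = (1 + rho)/2, so the working SD is 13 × sqrt((1 + rho)/2). Power at 83/166:

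| rho | SD | Power |
|---|---|---|
| unadjusted change | 13.00 | 81.3% |
| 0.4 | 10.88 | 92.6% |
| 0.5 | 11.26 | 90.8% |
| 0.6 | 11.63 | 89.0% |
| 0.7 | 11.99 | 87.1% |
| 0.8 | 12.33 | 85.2% |

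The equivalent gain in patients is 2/(1 + rho) − 1: 43% at rho 0.4 and 11% at rho 0.8.

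If 13 were instead the SD of pressure at a single time, the change SD would be 13 × sqrt(2(1 − rho)) and the ANCOVA SD 13 × sqrt(1 − rho²). Power for change score against ANCOVA would then be 74% and 87% at rho 0.4, 81% and 91% at 0.5, and 96% and 98% at 0.7. ANCOVA is ahead on either reading.

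**The case against.** **The analysis would still run.** A reader might infer that the rule is impossible to execute. It is not: a variable that cannot be transformed remains non-normal and passes to Mann-Whitney. The transformation sentences also lead into how variables are summarised, so applying them to the test of change is a reading, though the natural one because the primaries are not exempted. Raw pressures are positive and could be logged, but the contrast would no longer be a mean change in mm Hg. What stands is the mismatch with 4.1.

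**The share affected depends on sign.** Coding change as follow-up minus baseline makes 65% to 78% of values negative, which invites the claim that most patients cannot be transformed. The only scale that 12.1 quantifies is reduction, where the share is 22% to 35%.

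**The pre-test does little harm to error rates.** This is the strongest point against. Simulating the rule without its transformation step (Shapiro-Wilk on the pooled data, then t-test or Mann-Whitney) with normal, t(8), t(5) and skewed data gives type I error of about 5% to 6% and power of about 81% to 88%, against 81% to 82% for the plain t-test. It stands in full: the objection to the pre-test is about what is estimated and reported. The non-normal shapes are also assumptions that nothing in the protocol suggests.

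**The unadjusted test is legitimate.** Under randomisation it is unbiased, the change already subtracts baseline, and it reaches the planned power. That stands.

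**Detail may sit in a SAP.** Covariates and the use of interim visits are often settled there. But 12.2 does more than stay silent: it prescribes this sequence, and a SAP naming another primary analysis would contradict it.

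**Conclusion.** The point holds in a limited form. Section 12.2 does not fix, for the primary blood pressure changes, one analysis that estimates the difference in mean change set in 4.1 and used in 12.1. Its transformation step is undefined for about 22% to 35% of patients, given SD 13, approximate normality and an assumed mean reduction of 10 to 5 mm Hg. Its fallback changes the quantity compared, and the four comparisons can diverge.

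The missing baseline adjustment is an inefficiency. With 13 as the SD of change, power at 83/166 is 81% unadjusted and about 85% to 93% with ANCOVA for rho of 0.8 to 0.4, where rho and equal variances are assumed.

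Two stronger readings are not supported. A reader might infer that the trial is underpowered; if 13 is the SD of change, it is not. A reader might also infer that the interim ambulatory recordings go unused. The protocol does not say so: the 6-month value is a secondary outcome (9.2), and the imputation mentioned in 12.2 could draw on the others.

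**What to change.** In 12.2, add a primary analysis statement ahead of the general rule:

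- Each primary comparison (24-hour systolic, 24-hour diastolic, clinic systolic, clinic diastolic) is analysed by ANCOVA of the 1-year value on arm and the baseline value of the same measure, reporting the adjusted mean difference in mm Hg with its 95% confidence interval.
- The blood pressure endpoints are exempt from the Shapiro-Wilk rule and from transformation.
- A rank-based test of the change is a sensitivity analysis only.
- The sentence on exploring regression models does not apply to the primary comparisons.

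With the same baseline covariate, modelling the 1-year value or the change gives the same adjusted arm difference, so 4.1 and 9.1 can stand as written. All four comparisons must be named; a statement for 24-hour systolic pressure alone would leave three without a model. A site term, or a repeated-measures model on the scheduled ambulatory recordings with the 1-year contrast, is optional.

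The cost is an amendment to the wording of 12.2. It needs no extra patients, visits or measurements, and should be made before outcome data are examined by arm.

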7.5.3 Clinic based blood pressure monitoring

- Clinic based blood pressure assessment will be done by a trained nurse/doctor at the time of each study visit in both the groups.

Instructions to be followed while measuring blood pressure

- Blood pressure should be measured in a comfortable room and sitting position after resting for at least 5 minutes.
- At the time of initial evaluation measure BP in both the arms. If the difference between both the arms is > 10 mm Hg use the arm with the higher measurements. If the difference is > 20 mm Hg consider further evaluation.

- The same arm should be used preferably for all subsequent BP measurements.
- Take 3 readings at an interval of 1 min and the average of the last 2 measurements should be taken
- Patients should be instructed to avoid any stimulants such as coffee, tea, smoking or exercise 30 to 60 minutes before the measurement. Instruct the patient to empty the bladder.

7.6 Patient follow up and study period:

Patients will be followed up one month after randomisation followed by every 3 months till the end of 2 years or patient withdrawal. Details of the schedule of assessment is included in annexure

8. Schedule of activities assessment (refer annexure)

9. Study endpoints & outcomes

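### Four co-equal primary comparisons are each tested at p<0.05 with no success rule, while the sample size covers one systolic comparison whose measure is not named

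*Protocol*

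**What the plan says.** Section 4.1 lists two primary objectives: "To compare the mean change in systolic and diastolic 24 hr blood pressure ambulatory from baseline to 1 year between the 2 groups" and "To compare the mean change in systolic and diastolic blood pressure clinic based from baseline to 1 year between the 2 groups". Section 9.1 gives both measures the same rank: "Primary outcome will be change in blood pressure as measured by ambulatory blood pressure monitoring at the end of 1 year", and then "Primary outcome will be a change in blood pressure as measured in the clinic at the end of 1 year". The design synopsis has a single primary outcome entry, with a footnote that it covers the ambulatory and the clinic measure.

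On testing, section 12.2 says only "For statistical significance, two tailed p values <0.05 will be considered". It gives no order of testing, no division of alpha, and no statement of whether one significant result or all of them make the trial a success. It also says "Analysis will be carried out for the Intention to treat population as well per protocol population", without naming either population as the main one.

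On size, section 12.1 begins: "Sample size is calculated based on the expected difference in mean reduction in systolic blood pressure at the end of 1 year". It takes a difference of 5 mm Hg, SD 13 mm Hg, 80% power, 5% alpha and 1:2 allocation. This gives 83 and 166 patients, raised to 104 and 208 for 20% dropout. It does not say which systolic measure the 5 and the 13 describe.

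**The concern.** A trial with several primary comparisons needs a rule that turns their results into one conclusion, and its error rate and power follow from that rule. Here there are four comparisons of equal rank, one unadjusted threshold and no rule. The stated 5% and 80% belong to one systolic comparison, and the protocol does not identify which of its two systolic comparisons that is.

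The practical risk is choice after the fact. With one significant result among four, the sponsor could report a positive primary outcome, and a critic could say with equal support from the text that the primary objective failed. The choice of measure matters because the trial is open label (section 7.2). Clinic pressure is taken in person ("Clinic based blood pressure assessment will be done by a trained nurse/doctor at the time of each study visit in both the groups"), while ambulatory readings depend less on the observer. As written, a significant clinic result alone could be presented as primary success.

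**Working it through.** **Inputs from the protocol.** Difference 5 mm Hg, SD 13 mm Hg, alpha 5%, power 80%, ratio 1:2, evaluable 83/166, dropout 20% (section 12.1); two-tailed 0.05 (section 12.2); four comparisons (section 4.1). Section 9.1 also lists daytime and night-time ambulatory values. They are not counted, because 4.1 confines the ambulatory objective to the 24-hour mean.

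**Assumptions.** The protocol gives no correlations between the four measures, so a common correlation from 0 to 0.9 is used. It gives no diastolic or measure-specific effect, so 5/13 is applied to all four.

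**Step 1: the protocol's own figure.** Standard-care n = (1 + 1/2) × [13 × (1.960 + 0.842)/5]² = 79.6, so 80/160 by the normal approximation. The t-test solution is 80.2, so 81/162. The stated 83/166 is slightly larger. At 83/166 the noncentrality is 5 / [13 × √(1/83 + 1/166)] = 2.861, giving power of 81.6% (normal) or 81.3% (noncentral t). Dropout: 83/0.8 = 103.75, so 104; 166/0.8 = 207.5, so 208. For one systolic comparison, the stated size is sound.

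**Step 2: four comparisons, each at 0.05.** With independence, the chance of at least one false positive is 1 − 0.95⁴ = 18.5%, and the chance that all four succeed is 0.816⁴ = 44.4%. For correlated statistics, simulation of four normal statistics (1,000,000 draws, noncentrality 2.861 for power) gives:

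| Common correlation | Error if any one suffices | Power if any one suffices | Power if all four required |
|---|---|---|---|
| 0 | 18.5% | 99.9% | 44% |
| 0.3 | 17.5% | 98.8% | 53% |
| 0.5 | 15.6% | 97.2% | 58% |
| 0.7 | 13% | 94.5% | 64% |
| 0.8 | 11.4% | 92.5% | 68% |
| 0.9 | 9.4% | 89.6% | 72% |

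The error column assumes no true difference on any of the four. If all four are required, the type I error is at most 5%.

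**Step 3: a structured correlation.** With systolic-diastolic correlation 0.5 to 0.7 and ambulatory-clinic correlation 0.3 to 0.6 (also assumed), the any-one error is 14% to 17% and the all-four power is 54% to 61%.

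**Step 4: sensitivity to the diastolic effect.** At correlations 0.6 and 0.5, all-four power is 58% with equal standardised effects. It is about 42% if the diastolic effect is 0.8 times the systolic one, and about 67% if it is 1.2 times.

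**Step 5: what other rules would need.** Bonferroni over four (0.05/4 = 0.0125) leaves 63.5% power per comparison at 83/166 (noncentral t). Restoring 80% takes 114/228 evaluable, and 114/0.8 = 142.5, so 143/286 randomised. Requiring all four with 80% joint power takes about 129/258 evaluable at correlation 0, 119/238 at 0.5 and 105/210 at 0.8. One named primary with the others ordered behind it leaves 83/166 adequate for that primary, provided 5 and 13 apply to it.

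**The case against.** **A separate statistical analysis plan could supply the hierarchy.** It could, before analysis. But the protocol does more than stay silent: it fixes four comparisons of equal rank, one flat threshold and a sample size that identifies none of them. Those statements need amending wherever the detail is later placed.

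**The synopsis can be read as requiring both measures.** Its single entry covering both might mean that both must succeed, which would remove the error inflation from having two measures. It may equally mean only that both are measured. If both are required, the shortfall moves to power, which 12.1 does not address.

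**A reader might infer that both the 5% and the 80% fail.** They do not fail together under any single unadjusted rule. If any one result suffices, the error rises but the chance of at least one success stays at about 90% or more. If all four are required, the error holds and only power falls. For the one comparison that was sized, both figures hold.

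**A reader might infer that analysing two populations doubles the error.** The populations overlap heavily. With an assumed correlation of 0.90 to 0.95 between them, and 0.5 to 0.7 between endpoints, all eight tests together give about 16% to 21%, against 13% to 16% for the four alone. Nor does section 12.2 say that a per-protocol result can by itself establish success. It is enough to name the main population.

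**A reader might infer that clinic readings are biased.** The protocol says the trial is open label and that a nurse or doctor measures; it does not say whether that person knows the arm. Bias is not shown. The point bears only on which measure is the better single primary.

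**Conclusion.** The point stands in this form: four co-equal primary comparisons, each at two-tailed 0.05, have no ranking or success rule, and the sample size covers one systolic comparison without saying which. Either the family-wise error is about 9% to 19% instead of 5% (any one suffices), or joint power at 83/166 is about 44% to 72% instead of 80% (all four required). Which of the two applies cannot be settled from the text.

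The ranges rest on assumed correlations of 0 to 0.9, and the power range also on the same standardised effect for every comparison. The direction does not depend on the assumed correlation: even at 0.9, the error is nearly twice nominal or joint power is below 80%. A narrower statement, such as a threefold error rate, would need correlations that the protocol does not give. This should be settled before analysis, because it determines what result counts as success.

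**What to change.** In sections 4.1, 9.1 and 12.2 and in the synopsis, name one primary comparison. Change in 24-hour ambulatory systolic pressure from baseline to 1 year, in the intention-to-treat population at two-sided 0.05, is the natural choice in an open-label trial. Test the other three in a stated fixed order at 0.05 each, for example 24-hour diastolic, clinic systolic, clinic diastolic, and stop confirmatory testing at the first non-significant result. Make the per-protocol analysis supportive.

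In section 12.1, state which systolic measure the 5 mm Hg and the 13 mm Hg describe, and confirm or restate the power for the named primary. It would not be enough simply to declare that the existing 80% refers to ambulatory pressure, because the protocol does not show that those figures came from ambulatory data.

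The cost is a wording amendment. If 5 and 13 apply to the named primary, 83/166 remains adequate and no patients are added; if not, the size must be recalculated. The downside is small: clinic and diastolic pressure lose stand-alone primary status and can support a confirmatory claim only if the comparisons ahead of them succeed.
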